Our objective is to determine the effect of and compare two different doses of IV dexamethasone given preoperatively before TKA, when compared to placebo, using the outcome measures listed below:

Primary Outcome Measures

- To assess patient reported visual analog pain scores.
- To assess patient controlled analgesic usage.

Secondary Outcome Measures

1. To assess the soft tissue swelling about the operative knee after steroid administration.
2. To assess postoperative glucose levels after steroid administration.
3. To assess rehabilitation parameters such as postoperative knee range of motion and time to physical therapy clearance.
4. To assess incidence of nausea and vomiting postoperatively after steroid administration.
5. To assess patient satisfaction and function scores at 4 months with both Short Form (SF) – 12 and Knee Injury and Osteoarthritis Outcome Score Short Form (KOOS, Jr.) scores.
6. To assess hospital admission characteristics such as length of stay and rate of readmission.
7. To assess the risk of infection at 4 months and wound drainage at 7 days after perioperative steroid administration in total knee arthroplasty.

Study Design and Methods

We plan to conduct a prospective, double-blinded, randomized, placebo-controlled trial to evaluate perioperative glucocorticoid administration in total knee arthroplasty. There will be three arms in the study: 1) Placebo, 2) 10 mg dexamethasone, and 3) 20 mg dexamethasone.

Consent to Participation in the Study

Patients will be given the opportunity to participate in the study at the time of consent for surgery and blood product, which typically takes place in clinic during an evaluation for severe end-stage arthritis. It will be emphasized that study participation is optional, and that patients may be randomized to the control or placebo group. Patients will sign the combined informed consent and HIPAA form in order to participate in the study.

Method of Randomization

Once a patient chooses to be part of the study, he/she will be randomized in a blocked fashion to either the control group or to one of two intervention groups. Randomization will occur after informed consent has been obtained from the patients and after the preoperative screening examination is complete. Patients and investigators will be blinded to the randomization assignment. Emory's Investigational Drug Services will randomize each patient prior to dispensing the blinded dexamethasone/placebo doses.

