2. **Opioid analgesic usage:** The amount of each patient's postoperative opioid analgesic usage (converted into milligrams of morphine equivalents per day) will be recorded throughout the duration of their hospital stay. After inpatient discharge, this data will be collected using the smart device app. Patients will track the use of both prescribed narcotic medications and over the counter non-steroidal anti-inflammatory medications use for knee pain. Once patients are discharged from the hospital, they will be asked each day to enter their medication usage from a preloaded list (number of pills/day). Patients may also choose to enter other medications not on the list. This information will be recorded for the two-week postoperative period.
3. **Soft tissue swelling:** Soft tissue swelling will be evaluated using a measurement of knee circumference at the midpoint of the patella, with the knee in the maximum amount of extension allowed by the patient. This

measurement will be completed twice, and the average of the two measurements will be used as the value for that day. Knee circumference will be measured at baseline (time of enrollment), at POD 1 and each subsequent in-hospital POD, and at each follow up visit. The measurements obtained at baseline and at each clinic visit will be conducted by the research coordinator or physician. Postoperative measurements obtained during the patient's hospital stay will be conducted by the physical therapy staff, during the first/morning therapy session of each day. The non-operative knee will also be measured at the time of enrollment to use as a reference.

4. **Range of motion (ROM):** maximum active and passive ROM allowed by the patient will be measured using a goniometer. This measurement is the amount of flexion and extension recorded in degrees. ROM will be measured at the following time points: preoperatively at baseline, at POD 1 and each subsequent in-hospital POD, and at each follow up visit. ROM will be measured on postoperative in-hospital days by a physical therapist, whereas ROM at clinic visits will be measured by the research coordinator or physician. If more than one ROM measurement is obtained during an inpatient day, the numbers will be averaged to create one value for that day.

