After the study is complete, statistical analysis will be performed using de-identified patient data to determine differences in primary and secondary outcomes. Repeated-measures analyses for VAS pain score (and change from baseline), knee ROM, functionality scores (SF-12 and KOOS, Jr.), and blood glucose will be done with a means model with SAS Proc Mixed (version 9, mixed linear models) providing separate estimates of the means by time on study (baseline, in hospital, day 7, and at 1,4 and 12 months after total knee arthroplasty) and treatment group (dexamethasone or control). A compound symmetry variance-covariance form among the repeated measurements will be assumed for each outcome and robust estimates of the standard errors of parameters will be used to perform statistical tests and construct 95% confidence intervals²⁶. T-tests will be used to compare the pairwise differences between the model-based treatment means (least-squares means) at each time point. Mean changes over time within a treatment group will be tested for linear trend. The model-based means are unbiased with unbalanced and missing data, so long as the missing data are non-informative (missing at random). A

dropout process is assumed to be missing at random if, conditional on the observed data, the dropout is independent of the unobserved measurements. Statistical tests will be two-sided. A p value < 0.05 will be considered statistically significant.

Adverse Event Reporting

At a six-month time point following initiation of the study, we will assess our results for any reportable adverse events, including postoperative infections. This data will be reported to the Emory Institutional Review Board (IRB). We will monitor for any adverse outcomes at each subsequent six-month interval.

Data Safety and Monitoring Plan

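### Knee swelling, the first-listed secondary outcome, is left out of the analysis model and no use is given for the operated knee's baseline circumference; adding both would improve precision at no cost in data.

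*Combined protocol and SAP*

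**What the plan says.** The Objectives list as the first secondary outcome: "To assess the soft tissue swelling about the operative knee after steroid administration". No metric or time point is attached to it.

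Data Collection, item 3, sets the measure: "Soft tissue swelling will be evaluated using a measurement of knee circumference at the midpoint of the patella". Two readings are taken each time, and the "measurement will be completed twice, and the average of the two measurements will be used as the value for that day". On timing, "Knee circumference will be measured at baseline (time of enrollment), at POD 1 and each subsequent in-hospital POD, and at each follow up visit". On the other leg, "The non-operative knee will also be measured at the time of enrollment to use as a reference"; how that reference is to be used is not stated.

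The Statistical Analysis section promises in general terms to examine the secondary outcomes, then names those that go into the mixed model: "Repeated-measures analyses for VAS pain score (and change from baseline), knee ROM, functionality scores (SF-12 and KOOS, Jr.), and blood glucose will be done" by that route. Swelling is not named, and only VAS pain carries a change-from-baseline version. The comparison is then described: "T-tests will be used to compare the pairwise differences between the model-based treatment means (least-squares means) at each time point". No baseline covariate is named for any outcome.

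**The concern.** Circumference at mid-patella reflects how large the knee is as well as how swollen it is. The difference in size between patients was there before surgery and was measured at enrolment. An analysis that does not use that measurement carries the size differences as noise.

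Swelling is a repeated continuous measure, like range of motion and glucose, which are both in the model, yet no method is given for it. Adding it to the list would not be enough, because the model described compares arm means at each time point without a baseline covariate.

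Two things are at stake. A real effect on swelling may be estimated too imprecisely to be seen, although the data needed to sharpen it are being collected. And with the metric left open, raw circumference, change from enrolment, or some ratio to the other knee could each be chosen after the data are known.

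**Working it through.** **The plan's own figure.** The Statistical Analysis section gives 47 per arm, 141 in total (3 × 47 = 141), for 90% power on a VAS difference of 1.5. No VAS SD is stated, so 47 cannot be reproduced independently. By the normal approximation it implies SD = 1.5 / [(1.960 + 1.282) × √(2/47)] = 2.24. This figure concerns pain. The plan states none for swelling, and nothing below alters the sample size.

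**Inputs.** From the documents: 47 per arm, two-sided 0.05. Assumed, because the documents give no values: between-patient SD of circumference, the true arm difference, and ρ, the correlation between enrolment and postoperative circumference of the operated knee. No dropout is assumed.

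**Formulas.** For a pairwise comparison at one time point, the variance of the arm difference relative to raw circumference is:

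- raw value: 1
- change from baseline: 2(1 − ρ)
- baseline as covariate: 1 − ρ²

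The standard error is SD × √(factor) × √(2/47). Power comes from the two-sample t-test with 92 degrees of freedom and noncentrality equal to difference / SE.

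**SD 4 cm, difference 1.5 cm.** Raw: SE = 4 × √(2/47) = 0.825 cm, noncentrality 1.5 / 0.825 = 1.82, power 44%.

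| ρ | 1 − ρ² | Variance cut | SE (cm) | Noncentrality | Power, covariate | 2(1 − ρ) | Power, change only |
|---|---|---|---|---|---|---|---|
| 0.5 | 0.75 | 25% | 0.715 | 2.10 | 55% | 1.00 | 44% |
| 0.7 | 0.51 | 49% | 0.589 | 2.55 | 71% | 0.60 | 64% |
| 0.8 | 0.36 | 64% | 0.495 | 3.03 | 85% | 0.40 | 81% |
| 0.9 | 0.19 | 81% | 0.360 | 4.17 | 98% | 0.20 | 98% |

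**Other assumptions.**

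- SD 3 cm, difference 1.0 cm: raw 36%; with the covariate 45%, 61%, 76% and 96% at the same four values of ρ.
- SD 3 cm, difference 2 cm: raw about 89%; with the covariate 96% at ρ = 0.5. Here there is little left to gain.

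**Change score against covariate.** Change alone gains nothing at ρ = 0.5 and does worse than the raw value below that (at ρ = 0.3 its factor is 1.40, against 0.91 for the covariate). Once baseline is a covariate, using change or the postoperative value as the response gives the same treatment estimate at a given time point. The covariate is therefore what supplies the gain.

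**The case against.** Much of the case on the other side is sound.

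- Averaging duplicate readings is good practice, and range of motion is handled in a similar way. The gap is in the Statistical Analysis section, not in that sentence of item 3.
- The documents nowhere say that baseline will be ignored. A reader might infer that it goes unused, but that is inference from silence. A baseline and a reference knee are both collected, and the general commitment to analyse secondary outcomes leaves room to use them. What can be said is that no use is specified.
- A reader might infer that body size swamps any effect, or that a chance imbalance in limb size would invalidate the result. The documents support neither. They give no SD, effect or correlation, and raw power can be high (about 89% in the last case above). Under randomisation, limb size balances in expectation, and chance imbalance is ordinary sampling error already counted in the standard error. The cost is precision, not bias or type I error.
- The higher values of ρ may be optimistic. Item 3 has enrolment and clinic measurements made by the coordinator or physician and inpatient ones by physical therapy staff, with the knee only as straight as the patient allows.
- Swelling is one of seven secondary items, the sample size rests on VAS pain, and the section is also silent on a method for opioid use, nausea, length of stay and infection.

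These points limit the claim without removing it. Swelling has no stated analysis, the only model described would compare raw means, and at every ρ tabulated the covariate version is more precise.

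**Conclusion.** The point holds as a free improvement. Swelling is recorded as absolute circumference, is missing from the modelled outcomes, and has no stated use for its own baseline. The planned model, if extended to it unchanged, would give an unbiased but needlessly imprecise comparison.

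The variance reduction depends only on ρ: 25% to 81% for ρ from 0.5 to 0.9. What that means for power depends also on the assumed SD and difference. It amounts to 11 to 55 percentage points at SD 4 cm and 1.5 cm, and much less where raw power is already near 90%. None of these inputs comes from the documents, so the figures show a range and do not forecast this trial's power. The primary outcomes and the 47 per arm are unaffected.

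**What to change.** In the Statistical Analysis section:

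1. Add operated-knee circumference to the outcomes in the repeated-measures model, with that knee's enrolment circumference as a covariate. For this outcome the enrolment value then leaves the list of response times.
2. Report baseline-adjusted differences for each dose against placebo and between the two doses at prespecified times: POD 1 first, then the clinic visits. POD 1 is the natural lead because later inpatient days are measured only in patients still in hospital.
3. Show change from enrolment descriptively if wanted, and state what the single enrolment measurement of the non-operative knee is for. It cannot show how the operated knee changed after surgery, so it does not replace that knee's own baseline.

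While editing, reconcile item 3, which has circumference measured at every follow-up visit, with Table 1, which has no 12-month mark for knee swelling.

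Cost: about two sentences for the analysis and one correction for the schedule. The analysis change needs no new measurements and no change in sample size.

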Therapeutic Intervention

Patients in the intervention arms will receive two doses of either 10 mg dexamethasone or 20 mg dexamethasone. The first dose will be administered preoperatively within three hours of surgery once the patient receives anesthesia. The second dose will be administered eight hours after the first dose in the inpatient setting by the nurse in that unit. The second dose will be administered using a piggyback setup. Patients in the placebo arm will receive two doses of saline/placebo.

This particular dosing is chosen based on available literature that suggests a safe and effective dose is between 4 and 20 mg of dexamethasone²⁵⁻²⁶.

The administration of either steroid or placebo will occur in a double-blinded fashion. For each study participant, two blinded doses will be sent over from Emory's Investigational Drug Service (IDS). Thus, neither the patient receiving the medication nor the health care professional administering the medication or collecting study outcome data will be aware of whether or not the patient received the steroid or the placebo.

Both the intervention and control groups will receive spinal anesthesia using lidocaine and a standard multimodal postoperative pain management regimen typically used for total knee arthroplasty. This regimen will be standardized across all three attending surgeons participating in the study. The standard multimodal pain management regimen will be as follows:

- Preoperative:
 - **Decadron: 10 or 20mg IV x 2 doses, 8 hours apart (if randomized to study group)**
- Intraoperative:
 - **Ropivacaine:** Given intraoperatively. Injection, subcutaneous tissue/skin. Administered in standard fashion. (300mg)
 - **Toradol:** 30mg q 6hr for 6 total doses. 1st dose given intraoperatively at incision. (15 mg if patient is >65 years of age. Patients with Cr >1.5 will not receive Toradol).
- Postoperative
 - **Tylenol:** 1000mg po q 8hr (scheduled)
 - **Oxycodone:** 5mg or 10mg q 3-4hr prn pain, If intolerant to Oxycodone: second agent line is Hydrocodone or Oral Dilaudid (Tylenol will be adjusted accordingly if patient receives Hydrocodone).
 - **IV Morphine (or Dilaudid):** 1 or 2 mg q 2hr prn breakthrough pain
 - **Morphine PCA:** only for failure of the above
 - **MS Contin:** 15 mg BID for two weeks

On postoperative day (POD) 1, patients will be transitioned to oral (PO) and intravenous (IV) medications on an as-needed basis with a regimen that will be standardized across all study participants.

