7. **Blood Glucose Levels:** The patient's blood glucose level will be recorded once preoperatively at the pre-anesthesia clinic visit several days before surgery, at POD 1 and at each subsequent in-hospital POD using a hemocue. These do not consist of extra blood tests, as blood draws at these time points are considered standard of care. This data is being collected because hyperglycemia is a potential complication of IV steroid use. If patients experience ketoacidosis or hyperglycemia greater than 300, the study drug/placebo will be discontinued.
8. **Functionality scores:** The Short Form (SF) – 12 and Knee Injury and Osteoarthritis Outcome Score Short Form (KOOS, Jr.) questionnaires will be administered to patients at the baseline visit and at each follow up clinic visit. Both of these standardized function questionnaires are well validated and widely accepted in the literature.
9. **Hospital length of stay and readmission:** We will record the length of each patient's hospital stay and any readmission to our hospital for the 12-month duration of study.
10. **Infection:** Patients will have standard follow up clinic appointments at 1 and 4 months after surgery, at which time the clinical presence of possible wound drainage and periprosthetic infection will be evaluated. Patients will be followed up to 1 year after surgery to monitor for latent infections.

Table 1: Outcome measure and data collection schedule

	Pre-operative clinic visit	Each inpatient day	7 day app usage	2 week app usage	1 month clinic visit	4 month clinic visit	12 month clinic visit
Consent, Enrollment, Randomization	X						
Pain assessment	X	X	X		X	X	X
Opioid usage		X					
Pain medication log			X	X			
Knee swelling	X	X			X	X	
Knee ROM	X	X			X	X	X
Physical therapy milestones		X					
Nausea/vomiting		X	X				
Blood glucose	X	X					
Postoperative infection/Wound drainage		X			X	X	X
Length of stay		X					
KOOS, Jr. and SF-12	X				X	X	X

Consent Process

Patients will be asked to participate in the study at a preoperative clinic visit. The risks, benefits and the optional nature of the study will be emphasized. Patients may withdraw from the study at any given time. Consent will be obtained from one or more of the following three people: the attending surgeon, the orthopaedic surgery resident, or the research coordinator.

Participant Selection

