This study will be conducted at Emory University Orthopaedic and Spine Hospital and Clinic. The investigators perform over 500 total knee arthroplasty procedures per year. We estimate 75% (375) of the patients will be eligible and be willing to participate in the study. The Department of Orthopaedics staff performs 10-20 clinical trials per year and therefore is well-trained and prepared to perform clinical trials of this magnitude.

Inclusion Criteria

1. Patients undergoing primary total joint arthroplasty of the knee
2. Adult patients ages 18-100 years
3. Patients must have smart phone and/or device for app usage

Exclusion Criteria

1. Current chronic steroid use
2. Patients undergoing revision knee surgery
3. Patients ambulating preoperatively with assistive devices
4. Patients with avascular necrosis of the operative knee
5. Patients with a history of an adverse reaction to glucocorticoid steroids
6. Patients unable to provide informed consent
7. Patients with inflammatory arthritis
8. Prisoners
9. Current smokers
10. Patients <18 years of age
11. Any patient with a complicated postoperative course that requires transfer to the Intensive Care Unit (ICU) or to another facility for further management will be removed from the study.
12. Any contraindication that would prevent the patient from being treated with the standard multimodal postoperative pain management regimen
13. History of infection of surgical knee.
14. Patients with diabetes.
15. Patients that have an intolerance to Toradol.
16. Patients that do not have smart phone and/or device for app usage

Statistical Analysis

In order to adequately examine our primary outcome measure of pain reduction, our target sample size was obtained by a power analysis using retrospective data. Assuming a mean difference in the VAS of 1.5 between placebo vs. low dose and 1.5 for low dose vs. high dose (or 3 between placebo and high dose), in order to achieve 90% power, we will need 47 patients per study arm. Thus, the total number of patients enrolled would need to be at least 141. Based upon historical data, we expect it to take 18 months to reach our target N of 141.

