A subject key listing name, medical record number (MRN), age, sex, and study number will be kept in electronic format on a password-protected, encrypted computer, as well as in the research binder stored in a secure locked file cabinet. Data will be collected on paper case report forms (CRFs) and using the smart device application. The CRFs will not have any identifiable subject information, only the study number and subject's initials. Data will be entered into REDCap, a secure, web based application for building and managing online surveys and databases, by a study team member. The database will be made available to all investigators electronically. Data analysis will be performed by the investigators on a password-protected computer.

Each subject's safety will be monitored by his/her physician/investigator as the study procedures are performed and follow-up visits are conducted. Information regarding complications and adverse events will be gathered at each of the study follow-up visits. During administration of the study drug or placebo, all patients will be under close monitoring by the anesthesia and/or nursing staff. Any difference in risk of infection between study groups will be assessed, and this data will be reported to the Emory IRB as necessary. We will also monitor for and report any adverse outcomes and report to the Emory IRB as necessary. Patients will be followed out to one year after surgery to ensure that the intervention is safe. Notification to the Emory IRB will be done according to the IRB's specific procedures.

No patient will be enrolled in the study and have any study-related procedures performed, including completing subject clinical assessments, before an approved Informed Consent Document is signed.

References

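### Readmissions are recorded only at the trial hospital, so the 12-month rate is understated and the absolute difference between arms shrinks toward zero; the risk ratio is not biased if capture is equal

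*Combined protocol and SAP*

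**What the plan says.** Secondary Outcome Measures, item 6, reads "To assess hospital admission characteristics such as length of stay and rate of readmission". It does not limit the hospital and gives no time window.

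Data Collection, item 9, gives the recording rule: "any readmission to our hospital for the 12-month duration of study". The 12-month window and the restriction to one hospital come from this sentence.

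Table 1 has a length-of-stay row, marked for inpatient days only, and none for readmission. The protocol describes no patient question, request for outside records or other check for admissions elsewhere.

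Under Participant Selection the trial has a single specialist site: "This study will be conducted at Emory University Orthopaedic and Spine Hospital and Clinic". The Statistical Analysis section names neither a method nor an effect measure for readmission.

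The Data Safety and Monitoring Plan adds that "Information regarding complications and adverse events will be gathered at each of the study follow-up visits". It does not mention readmission or link this information to the readmission outcome.

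**The concern.** The objective and the recording rule describe different quantities. One is the readmission rate; the other is the rate of return to one orthopaedic and spine hospital. Over 12 months some patients may be admitted elsewhere, and the rule as written does not count them. The reported rate would then be too low for the outcome named in the objectives.

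An absolute difference between arms would also look smaller than it is. That matters in both directions. The protocol follows patients for a year partly to establish safety, while its introduction names readmission as a consequence of poorly controlled pain, so the outcome bears on benefit as well as harm. Events will be few with 47 patients per arm, so each one lost costs precision.

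**Working it through.** **The plan's own figure.** The only computed design figure is for pain: "in order to achieve 90% power, we will need 47 patients per study arm". No standard deviation is stated, so 47 cannot be confirmed or refuted. With a difference of 1.5, two-sided 0.05 and the normal approximation it corresponds to an SD of 1.5 × √(47/2) / (1.960 + 1.282) ≈ 2.24. There is no design figure for readmission; 47 is used below only as the arm size.

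**Inputs.**
- From the documents: 47 patients per arm; two-sided 0.05; own-hospital recording over 12 months.
- Assumed, because the documents give no values: true 12-month risks of 5% on placebo and 10% on active; capture c (the share of readmissions that come back to the trial hospital) of 0.6 to 0.9, equal in both arms.

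**Formulas.** Write p0 and p1 for the true risks.
- Observed risks: c·p0 and c·p1. The rate is low by the fraction 1 − c, that is 10% to 40% over the assumed range.
- Observed difference: c·p1 − c·p0 = c·(p1 − p0).
- Observed risk ratio: (c·p1)/(c·p0) = p1/p0, so c cancels.
- Standard error of the log risk ratio, at expected counts e1 and e0: √(1/e1 + 1/e0 − 2/47).
- Power for one pair of arms: normal approximation for two proportions, pooled variance under the null.

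**Results.**

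| Capture c | Observed risks | Difference (points) | Risk ratio | Odds ratio | Expected events per 47 | SE of log risk ratio | Power |
|---|---|---|---|---|---|---|---|
| 1.0 | 10% vs 5% | 5.0 | 2.00 | 2.11 | 4.70 vs 2.35 | 0.77 | 15% |
| 0.9 | 9% vs 4.5% | 4.5 | 2.00 | 2.10 | 4.23 vs 2.12 | 0.82 | 14% |
| 0.6 | 6% vs 3% | 3.0 | 2.00 | 2.06 | 2.82 vs 1.41 | 1.01 | 10% |

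For example, at c = 0.6 the standard error is √(1/2.82 + 1/1.41 − 2/47) = √1.021 = 1.01, against √(1/4.70 + 1/2.35 − 2/47) = √0.596 = 0.77 at full capture, a rise of about 31%. Fisher's exact test has lower power still: about 6% at full capture and 3% at c = 0.7.

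**Direction.** Reverse the assumed effect, to 10% on placebo and 5% on active. The difference then goes from −5.0 points to −4.5 at c = 0.9 and −3.0 at c = 0.6. A benefit shrinks exactly as a harm does.

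**Unequal capture.** This is what would move the ratio, and it can go either way. With true risks of 5% and 10%, capture of 0.8 on placebo and 0.6 on active gives 6%/4% = 1.5; capture of 0.6 and 0.8 gives 8%/3% = 2.67.

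**The case against.** The strongest reply is that equal under-recording leaves the relative comparison intact. That stands. Treatment is randomised, and the protocol says that "neither the patient receiving the medication nor the health care professional administering the medication or collecting study outcome data will be aware" of the allocation. Roughly equal capture is the reasonable expectation, and nothing in the documents suggests otherwise.

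A reader might go further and infer that the rule biases the trial toward finding no harm. The documents do not support this. The shrinkage applies only to the absolute scale, the plan does not say which scale it will use, and a true benefit is hidden equally. Item 6 places readmission beside length of stay; infection and wound drainage are a separate item.

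A reader might also infer that infections treated elsewhere are lost to the trial. That is too strong. Table 1 schedules infection and wound drainage at 1, 4 and 12 months, and complications and adverse events are gathered at follow-up visits. Some outside admissions may surface that way. They would still not enter the readmission count, because item 9 limits that count to the trial hospital.

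Two further points have force. Own-hospital readmission is a legitimate outcome and can be verified from records, so renaming it would also remove the mismatch. And the loss is small in number: on the assumed rates, at 60% capture, about 1.9 events in one arm (4.70 − 2.82) and 0.9 in the other (2.35 − 1.41).

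**Conclusion.** The point holds in a limited form. Item 9 measures something narrower than the outcome in item 6, and no other part of the plan closes the gap. The all-hospital readmission rate is understated whenever a patient is admitted elsewhere.

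With equal capture, the absolute difference is attenuated toward zero by the factor c and precision falls, while the risk ratio is unbiased and the odds ratio barely moves. On assumed risks of 10% and 5% and capture of 60% to 90%, 5 points becomes 3.0 to 4.5. Both the risks and the capture are illustrative; the documents allow no estimate of either, so the true shortfall is unknown.

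The practical weight is modest. Readmission is a secondary outcome with no stated analysis, and a doubling from 5% to 10% has only about 6% (Fisher) to 15% (normal approximation) power per pair of arms even with full capture. Better recording will rarely change a test result. It will make the reported rate match its name, which is enough reason to act given how little it costs.

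**What to change.** Define the outcome in item 6 as readmission to any hospital within 12 months, and amend Data Collection item 9 to match. Ask every patient at the existing 1, 4 and 12 month visits about any hospital admission, with date and reason. Add a readmission row to Table 1 for those visits, and check own-hospital admissions against the medical record. Report own-hospital and any-hospital readmissions separately by arm, so that the record-verified count stays visible, and state the effect measure in the Statistical Analysis section.

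The cost is one case report form item at visits already scheduled. The downside is some reliance on patient report for outside admissions.

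If this is not done, rename the outcome as readmission to the trial hospital and limit the conclusion to that.
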